14.1. Derivations

Duration of exposure (weeks) = (date of last study treatment administration – date of first study treatment administration + 1) / 7. For subjects with missing Date of Last Dose on the End of Study eCRF, their date of last study treatment administration will be imputed by the last date of all dosing administration start/stop dates recorded.

15. STUDY TREATMENT COMPLIANCE

The total number of tablets expected, total number of tablets taken, total number of tablets missed, overall compliance with study treatment, and frequency and percentage of subjects with overall compliance of < 80% or > 120% will be summarized for the Safety Set for both the first 12 weeks and the entire study.

15.1. Derivations

Compliance to study treatment is based on the Drug Accountability eCRF and will be calculated as the total number of tablets taken (total dispensed – total returned) divided by the number of tablets expected during the Treatment Period, expressed as a percentage, refer to calculations below.

The total number of tablets expected is defined as the number of tablets that a subject is expected to have taken between their first and last study treatment administration and is numerically identical to the subject's overall study treatment exposure, since the medication is to be taken once daily. On any site visit day, the medication is to be held and taken at the site, after all predose assessments have been completed. For example, if a subject took their last dose of study treatment on Day 200 and returned to the site on Day 207 to return the study treatment bottle, then the total number of tablets expected would be 200, not 206.

- Overall compliance to study treatment will be calculated as follows; total number of tablets returned subtracted from total number of tablets dispensed, divided by the duration of treatment, multiplied by 100

For all bottles not returned, it will be assumed that all dispensed tablets were taken. For each subject, if a high percentage (> 25%) of bottles were not returned by a subject, additional analyses may be done where bottles not returned are excluded from the overall compliance calculation for the subject. In such analysis, the date of last dose or the date of last bottle return, whichever is earlier, will be used as the “date of last dose” in the calculation above.

Both scheduled and unscheduled study treatment dispensations will be used in the compliance calculation. Overall compliance calculations will be performed for both the 12-Week Treatment Period and the entire study and will be used in determining inclusion/exclusion of subjects in the respective Per Protocol Set. For subjects discontinued prior to Week 12, their overall compliance for the 12-Week Treatment Period and the entire study will be identical. For subjects who

remained in the study beyond Week 12, the 12-Week total tablets expected will be defined as Date of Week 12 visit – Date of first dose, since their last dose in the 12-Week Treatment Period should have been taken on the day before Week 12 visit.

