- ^e All subjects will complete TB screening to determine eligibility (refer to Appendix 2). The QuantiFERON TB Gold and tuberculin skin test should not be performed in subjects previously diagnosed with TB infection. The TB questionnaire will be completed for all subjects during the Screening period and at every study visit for subjects residing in countries with a high TB burden or MDR TB as identified by the WHO. For subjects who are receiving TB prophylaxis treatment, the TB questionnaire will be completed at every study visit (until TB prophylaxis treatment course is completed).
- ^f Subjects will be tested for HIV antibodies as well as HBV and HCV infection at screening (Section 9.10.7.1.3).
- ^g Subjects will begin eDiary entries beginning the first day of screening after eDiary training is completed. The eDiary should be completed daily to capture data including daily SF and RB (the 2 subject-reported outcome measures contributing to the calculation of the MMS), and study treatment administration. The subject eDiary will be reviewed by study site staff at each treatment visit.
- ^h The MMS will be calculated electronically at the Day 1 and Week 12/Early termination visits. The subscores for SF and RB are derived from the subject eDiary entries using the scores from the 3 most recent consecutive days within the 7 days prior to the day of bowel preparation (excluding the day of bowel preparation), averaged and rounded to the nearest integer (Section 9.3.10).
- ⁱ Stool frequency and RB subject-reported outcomes will be recorded daily using electronic subject eDiaries. The RB and SF subscores will be calculated as indicated in Section 9.4.2.
- ^j Safety vital signs (resting heart rate and systolic and diastolic BP, body temperature, and respiratory rate) taken with subjects in the sitting position will be performed at Screening and prior to randomization on Week 0/Day 1 (baseline). If the subject's heart rate is < 50 bpm, or systolic BP < 90 mm Hg, or diastolic BP < 55 mm Hg, or has symptoms of low HR or low BP, the subject must not be randomized and should be considered a screen failure.
- ^k On Day 1, vital sign assessments will be conducted as described in Section 9.4.2.1.

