5.4. Per Protocol Sets

The Per Protocol Set will be derived for Week 12 and Week 52, separately, and will consist of all subjects in the FAS who adhere to the protocol and complete Week 12 and Week 52, respectively. These sets will be used in sensitivity analyses of the primary and key secondary endpoints to evaluate the influences of important protocol deviations on the primary results.

Subjects may be excluded from the Week 12 Per Protocol Set if they meet any of the following criteria:

- Overall study treatment noncompliance in the first 12 weeks (< 80 or $> 120\%$)
- Receive incorrect study treatment for > 7 days in total in the first 12 weeks
- Use rescue medication (new or dose increase from the highest dose of background treatment for UC received during Screening) or undergo rescue medical procedure that may affect efficacy endpoint at Week 12

- Miss Week 12 endoscopic score (ES) in prespecified analysis window (per Section 6.4) for reasons other than UC flare, or discontinued due to disease worsening or lack of efficacy

Subjects may be excluded from the Week 52 Per Protocol Set if they meet any of the following criteria:

- Overall study treatment noncompliance (< 80 or > 120%)
- Receive incorrect study treatment for > 7 days in total
- Use rescue medication (new or dose increase from the highest dose received during Screening) or rescue medical procedure that may affect efficacy endpoint at Week 52
- Miss Week 52 ES in prespecified analysis window (per Section 6.4) for reasons other than UC flare, or discontinued due to disease worsening or lack of efficacy

Refer to [Appendix 7](#) for the definition of rescue therapies (medication and medical procedures). All protocol deviations will be reviewed in addition to the programmable deviations (eg, study treatment noncompliance) to determine if any deviation is significant enough to exclude a subject from each of the Per Protocol Sets. All exclusion flags will be finalized before study unblinding. Subjects excluded from each Per Protocol Set will be listed along with the reason category above. Subjects will be summarized by treatment to which they were randomized, regardless of treatment actually received.

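### SAP 15.1 can put a fully adherent subject who stops soon after dispensing and keeps the bottle above 120% compliance, and it partly masks missed doses from unreturned bottles

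*SAP*

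**What the plan says.** SAP 15.1 computes compliance as tablets dispensed minus tablets returned, divided by tablets expected.

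- **Tablets taken.** For missing bottles: "For all bottles not returned, it will be assumed that all dispensed tablets were taken".
- **Tablets expected.** These are the tablets a subject is "expected to have taken between their first and last study treatment administration". In the SAP's example the last dose is on Day 200 and the bottle comes back on Day 207: "then the total number of tablets expected would be 200, not 206".
- **Alternative.** The SAP adds that "if a high percentage (> 25%) of bottles were not returned by a subject, additional analyses may be done". Unreturned bottles are then left out, and the calculation ends at "the date of last dose or the date of last bottle return, whichever is earlier".
- **Use.** Compliance for the first 12 weeks and for the whole study "will be used in determining inclusion/exclusion of subjects in the respective Per Protocol Set". SAP 5.4 lists as a ground for exclusion from the Week 52 set "Overall study treatment noncompliance (< 80 or > 120" (per cent), with the same limits over the first 12 weeks for the Week 12 set. SAP 15 also tabulates subjects outside these limits.

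Protocol 6.6 bases compliance on tablet count. Daily dosing is recorded separately: Table 7, footnote g says "The eDiary should be completed daily to capture data including daily SF and RB", and the same sentence goes on to list study treatment administration.

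**The concern.** The numerator and denominator cover different periods when a bottle is not returned. The numerator takes in the whole last bottle, including tablets meant for days after the subject stopped. The denominator ends at the last dose. Ending it there is reasonable in itself; the fault is the mismatch.

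Two errors follow, in opposite directions. A fully adherent subject who stops early can be labelled as taking too much. A subject who missed doses from a bottle that never came back is credited with all of it.

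The first error bears on the Per Protocol Sets. Under the fourth exclusion criterion in SAP 5.4, a missing endoscopic score does not exclude a subject who stopped for worsening or lack of efficacy, and SAP 16.1.2 says such subjects may remain in the sets. They count as nonresponders, so a false reading above 120% could remove nonresponders from an analysis planned for both primary endpoints and all key secondary endpoints (SAP Table 3).

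**Working it through.** **The plan's own figure.** Expected tablets = last dose day − first dose day + 1 = 200 − 1 + 1 = 200. Counting to the day before the Day 207 visit would give 206. The SAP's 200 is reproduced, so the denominator does stop at the last dose.

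**Inputs.** Dispensing visits are Day 1 and Weeks 2, 4, 8, 12, 16, 20, 24, 32, 40 and 48 (Protocol Tables 7 and 8). The limits are 80% and 120% (SAP 5.4). Tablets per bottle are not given. The main examples assume supply equal to the days until the next visit, hence 28 tablets per four weeks, in one bottle per visit.

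**When a false reading arises.** Let D be days on treatment with every dose taken, and U the unused tablets in unreturned bottles. Reported compliance = (D + U)/D, which exceeds 120% when U > 0.20 × D.

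- Day 60 stop, Week 8 bottle kept: (56 + 28)/60 = 84/60 = 140%. U = 24 against 0.20 × 60 = 12. Unreturned share 1/4 = 25%, which is not above 25%.
- Day 90 stop, Week 12 bottle kept: (84 + 28)/90 = 112/90 = 124%. U = 22 against 18. Unreturned share 1/5 = 20%.
- Day 200 stop, 60 tablets from Week 24 kept (a different pack assumption): (168 + 60)/200 = 228/200 = 114%, not flagged.

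**Range over assumed bottle sizes.** Two bottles are assumed at each eight-week dispensing for the 28-, 30- and 35-tablet sizes, otherwise one. Earlier bottles are reconciled, and the supply from the last dispensing visit is kept. Stop days from Day 57 on that give more than 120%:

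| Tablets per bottle | Stop days flagged |
|---|---|
| 28 | 57–69, 85–93, 113–116, 169–186, 225–233 |
| 30 | 57–71, 85–94, 113–118, 141, 169–189, 225–236, 281–283 |
| 35 | 57–75, 85–99, 113–122, 141–145, 169–198, 225–244, 281–291 |
| 60 | 57–166, 169–189, 225–236, 281–283 |

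No stop after the Week 48 dispensing is flagged under any of these. In every row the unreturned share is at most 25%, so the alternative is not triggered. For stops before Day 57 the share is 33% to 100%, and the alternative may be done.

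**Masking.** Let f be the share of bottles unreturned and c the true compliance, with missed doses spread evenly and dispensed equal to expected. Reported = (1 − f) × c + f.

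- f = 0.25, c = 0.75: 0.5625 + 0.25 = 81.3%, not flagged.
- f = 0.25, c = 0.70: 0.525 + 0.25 = 77.5%, still flagged.
- Break-even at f = 0.25: (0.80 − 0.25)/0.75 = 73.3%.
- Concentrated case: 3 of 13 equal bottles (23%) unreturned and untouched gives true 10/13 = 76.9%, reported 100%.

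**Which set is reached.** SAP 15.1 makes 12-week and whole-study compliance identical for a stop before Week 12, so the Day 60 subject's 140% bears on both Per Protocol Sets. For the Day 90 subject, 12-week compliance is 84/84 = 100%, so only the Week 52 set is in question.

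**Whether the existing alternative would do if made mandatory.** For the Day 60 stop it gives 56/57 = 98%, which is sound. Read literally, it fails for bottles missing mid-study, because it drops their tablets but shortens only the end date. A fully adherent subject at Week 12 with the Week 2 and Week 4 bottles missing (2 of 4) would compute as (14 + 28)/84 = 50%.

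**The case against.** The protocol is built to get bottles back. Early stoppers attend a termination visit within 7 days of the last dose (Protocol 5.1), tablets are collected at each visit (8.4), and bottles counted by video must be returned at the next onsite visit (9.6). If the bottle comes back there is no distortion. The documents do not say how often it fails to. This stands, and it limits the size of the problem.

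Exclusion is not automatic. SAP 5.4 says subjects may be excluded, after review of all deviations and before unblinding, so a reviewer could recognise a 124% reading caused by one missing bottle. SAP 5.4 also opens by confining each set to subjects who completed Week 12 or Week 52, which sits awkwardly with keeping early stoppers at all. Both points weaken the Per Protocol consequence. They do not remove it, since the fourth criterion and SAP 16.1.2 allow stoppers for worsening to stay, and nothing tells the reviewer to discount the reading.

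Other controls catch some missed doses: between-visit counts outside 80% to 120% are recorded as deviations and discrepancies with the eDiary are noted (Protocol 6.6), and dose interruptions are summarised (SAP 14). A reader might infer that noncompliance is hidden outright. The documents do not support that: masking is in proportion to the unreturned share, and true 70% with a quarter of bottles missing is still flagged.

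A reader might also infer that eDiary dosing should replace the count. Protocol 6.6 names tablet count as the basis, and the eDiary is self-reported, so it can serve only as a supporting check.

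**Conclusion.** The point holds in a limited form. The stated rule gives a wrong compliance figure for a definable group: subjects who stop soon after dispensing, do not return that bottle, and leave unused tablets exceeding 20% of their days on treatment. For them the reading can be 124% to 140% in the two main examples, against a true 100%. It also understates noncompliance in proportion to the unreturned share. The optional alternative does not cure either error: it misses one bottle in four or more, and the SAP does not say that its result replaces the main figure for the Per Protocol flag.

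It would be too strong to say that early stoppers in general are flagged. Late stops mostly stay under 120%, and returned bottles cause no error. Nor is the primary result at risk: that analysis uses the FAS with Baseline MMS 5 to 9, and only the compliance tables and supplementary Per Protocol analyses are affected. The percentages rest on assumed pack sizes, and the number of subjects is unknown. This is a minor point, worth correcting because the correction is cheap.

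**What to change.** In SAP 15.1, for any unreturned bottle, remove its dispensing interval by default from both tablets taken and tablets expected. The Day 60 stop becomes 56/56 = 100% and the Day 90 stop 84/84 = 100%. With evenly spread missed doses, true 75% reads 75%. At the least, cap the imputed tablets at the days from dispensing to last dose: (56 + 4)/60 and (84 + 6)/90, both 100%. The cap cures the false excess but not the masking.

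State that this figure drives both the table of subjects below 80% or above 120% and the Per Protocol flag. Use the eDiary dosing record as a supporting check only. Say how a subject with no returned bottles is reported, since removal then leaves nothing to compute.

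The cost is a few lines of SAP text and a small derivation, to be settled before unblinding. The downside is that removing an interval uses less data and does not reveal missed doses within it: the 3-of-13 case would still read 100%.

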16. EFFICACY OUTCOMES

Unless otherwise stated, the primary efficacy analyses will be based on subject stratum used at the time of randomization for the FAS with Baseline MMS 5 to 9. Primary and key secondary efficacy analyses will be repeated for all subjects in FAS with Baseline MMS 4 to 9 as a supplementary analysis. The following definitions will be used to assess efficacy outcomes:

- Clinical response: A ≥ 2 -point and $\geq 30\%$ decrease from Baseline in MMS, and a ≥ 1 -point decrease from Baseline in RB subscore or an absolute RB subscore ≤ 1
- Clinical remission: SF subscore = 0 (or = 1 with a ≥ 1 -point decrease from Baseline), RB subscore = 0, and ES ≤ 1 (excluding friability)
- Endoscopic improvement: ES of ≤ 1 (excluding friability)
- Endoscopic normalization: ES = 0
- Mucosal healing: ES of ≤ 1 (excluding friability) with histologic remission measured by a Geboes Index score < 2.0
- Symptomatic remission: SF subscore = 0 (or = 1 with a ≥ 1 -point decrease from Baseline) and RB subscore = 0
- Complete symptomatic remission: SF subscore = 0 and RB subscore of 0
- Symptomatic response: Decrease from Baseline $\geq 30\%$ in composite RB and SF subscores
- Noninvasive clinical response: A $\geq 30\%$ decrease from Baseline in composite RB and SF, and a ≥ 1 -point decrease from Baseline in RB subscore or an absolute RB subscore ≤ 1
- Histologic improvement: Geboes Index score ≤ 3.1
- Histologic remission: Geboes Index score < 2.0
- Histologic improvement using Roberts Histopathology Index (RHI): $\geq 50\%$ reduction from Baseline in RHI or RHI ≤ 3
- Histologic remission using RHI: RHI ≤ 3 , with scores of 0 (zero) for both Geboes Grade 2B (lamina propria neutrophils) and Grade 3 (neutrophils in epithelium)
- Histologic improvement using Nancy Histologic Index (NHI): ≥ 1 point reduction from Baseline NHI
- Histologic remission using NHI: ≤ 1

- Clinical remission using total Mayo Clinic score: total Mayo Clinic score of ≤ 2 points with no individual subscore of > 1 point
- Clinical response using total Mayo Clinic score: $A \geq 3$ -point and $\geq 30\%$ decrease from Baseline in total Mayo Clinic score, and a ≥ 1 -point decrease from Baseline in RB subscore or an absolute RB subscore ≤ 1
- Corticosteroid-free clinical remission: Clinical remission at Week 52 and who had not been receiving corticosteroids for ≥ 12 weeks prior to Week 52
- Sustained clinical remission: Clinical remission at both Week 12 and Week 52
- Loss of response:
 - Achieved clinical response at Week 12
 - $A \geq 2$ -point increase from Week 12 in the combined SF + RB scores and combined SF + RB score of ≥ 4 , on 2 consecutive visits (≥ 7 days apart), and
 - Confirmed by centrally read ES ≥ 2

16.1. Primary Efficacy

16.1.1. Primary Efficacy Variables and Derivations

The primary efficacy endpoints will compare etrasimod to placebo for:

- The proportion of subjects achieving clinical remission at Week 12
- The proportion of subjects achieving clinical remission at Week 52

Clinical remission is defined in Section 16. The SF, RB, and ES subscores will be based on the Mayo Clinic score eCRF. Subjects who achieve clinical remission will be referred to as responders. Subjects who do not achieve clinical remission will be referred to as nonresponders.

Multiplicity adjustments for the coprimary endpoints are discussed in Section 8.4.

16.1.2. Missing Data Methods for Primary Efficacy Variables

Subjects who 1) discontinue the study for worsening of disease, lack of efficacy, or adverse event related to UC, 2) initiate a rescue medication for UC, 3) have an increase in dose over Baseline levels in their existing UC medication, or 4) have rescue medical procedure (eg, colectomy, ileostomy, or sigmoidectomy) during the study as confirmed after blinded review by clinical and medical team members before study unblinding will be considered to have a known (ie, nonmissing) outcome of nonresponse in the analysis of all efficacy endpoints at any subsequent timepoints, including the primary endpoint. The rescue medications will be identified by the Arena clinical team during blinded data review. Refer to [Appendix 7](#) for the definition of rescue therapies (medication and medical procedures). In scenarios 2 and 3 above, if a subject has an efficacy measurement collected after the initiation or dose increase from Baseline of UC medication, the observed data will be censored at the time of initiation or dose increase and they will be considered as having a nonresponse. Subjects in all 4 scenarios above may still be included in the respective Per Protocol Set, provided they do not violate other criteria for Per

Protocol Set. For example, they will be excluded from the respective Per Protocol Set if they initiate a prohibited medication before the Week 12 or Week 52 efficacy assessment that can affect efficacy of the study treatment and the indication is unrelated to UC.

Analysis visits will be mapped as per Section 6.4 before any missing data imputation method is applied.

Subjects with a missing efficacy outcome will be included in the primary analyses using the following missing data methods:

- Primary method: Single imputation as nonresponder
- Sensitivity analyses: Multiple imputation under missing at random (MAR), tipping point analysis, multiple imputation with Copy Reference (CR) under missing not at random (MNAR), and a hybrid imputation with multiple imputation to handle missing endoscopy data due to the COVID-19 pandemic impact and nonresponder imputation (NRI) for missing data not due to the COVID-19 pandemic impact. More details are provided in Section 16.1.4
- Supplementary analyses: mFAS analysis with data as observed, Per Protocol Set analysis (Week 12 Per Protocol Set for Week 12 endpoints and Week 52 Per Protocol Set for Week 52 endpoints)

